7.3 Medical History

Relevant medical conditions will be coded using the Medical Dictionary for Regulatory Activities (MedDRA). The MedDRA version used for reporting will be specified as a footnote in the applicable tables and listings.

The relevant medical conditions will be tabulated separately for active (ongoing) and not-active conditions by system organ class (SOC) and preferred term (PT). Medical history events will be marked as ongoing if still active at time of informed consent.

7.4 Prior Cancer Related Therapy

Descriptive statistics with respect to prior therapy will be displayed. A listing of all data recorded on the Prior Cancer Related Surgery, Prior Radiotherapy and Prior Cancer Systemic Therapy CRF pages will also be provided.

Prior cancer related surgery will be coded using the Medical Dictionary for Regulatory Activities (MedDRA) and prior cancer systemic therapy will be coded using the WHO Drug Global dictionary. The MedDRA and WHO Drug Global dictionary versions used for reporting will be specified as a footnote in the applicable tables and listings.

The variables to be summarized in tables are:

- Prior Prostate Cancer-related Surgery
 - Number of patients with at least one prostate cancer-related Surgery (including biopsies)
 - Prior number of prostate cancer-related surgeries/biopsies
 - Reason for prior surgery (Therapeutic, Diagnostic/Biopsy, Palliative, Other)
- Prior Prostate Cancer-related Radiotherapy
 - Number of patients with at least one Prostate Cancer-related Radiotherapy
 - Prior number of radiotherapies
 - Unique Sites
- Prior Prostate Cancer-related Systemic Therapy: All Therapies
 - Prior number of NAAD-containing regimens
 - Prior number of taxane-containing regimens
 - Reason for therapy
 - Number of unique agents
 - Type of prior therapy (by ATC Level 4 and WHO Drug preferred name). Type of prior therapy will be presented by ATC level alphabetically and preferred name is sorted within ATC class alphabetically.
- Prior Prostate Cancer-related Systemic Therapy: Last Taxane Therapy
 - Last taxane therapy is defined as the last taxane as part of a taxane-containing regimen, prior to study entry.
 - Reason for Therapy
 - Number of cycles
 - Duration of therapy (months): (last taxane therapy stop date – last taxane therapy start date + 1)/30.4375. Incomplete dates will not be imputed.
 - Progression
 - PSA progression (yes, no, not applicable, unknown)
 - Bone progression (yes, no, not applicable, unknown)
 - Soft tissue progression (yes, no, not applicable, unknown)
 - Type(s) of progression (New lesions, existing lesions, new and existing lesions, not applicable, unknown)
 - Treatment-free interval (months, defined in Section 5.6)
 - Best overall response (BOR) to last taxane-therapy (Complete response (CR), Partial response (PR), Stable disease (SD), Progressive Disease (PD), Not Available, Unknown)
 - Duration of historic BOR (CR or PR) (months): (date of progression (earliest of PSA, bone or soft tissue) - date of best response (CR or PR) + 1)/30.4375. Incomplete dates will not be imputed.
 - Reason last taxane therapy ended

7.5 Sub-study

Baseline demographics and baseline disease characteristics will be summarized for the Sub-study Safety Analysis Set and will be summarized and listed for PSMA-11 sub-study analysis set. Medical history and prior cancer therapy will be listed for the PSMA-11 Sub-study Analysis Set.

8. Efficacy Evaluation

8.1 Efficacy Variable Definitions

In general, time to event and duration endpoints (e.g. rPFS), in number of days, is calculated as:

Days = event/censor date – reference date (e.g. randomization date) +1. If a patient has no assessment after first dose, censoring is at date of randomization. See Section 5 for converting time units.

Radiographic imaging will be assessed locally by each site and entered into the CRF. Additionally, patient scans will be collected for independent central review and data will be entered into the imaging CRF at the vendor. The independent central review will be used for the primary analyses of radiographic progression-free survival per PCWG3, overall response rate, disease control rate and duration of response using RECIST 1.1 and progression-free survival. The final radiology assessment as determined by the independent reviewer and described in the imaging review charter will be used for the analysis of these endpoints. At the time of analysis and prior to database lock, the two independent radiologists (radiologist 1 and radiologist 2) will each perform a global read and make a final determination of rPFS for the patient. If there is a difference in patient level determination of progressive disease (PD) between the two independent radiologists, a third radiologist will adjudicate the final assessment. The adjudicator will select which of the two independent radiologists' reads (radiologist 1 or radiologist 2) he/she agrees with more for RECIST/PCWG3 PD determination. The selected radiology read (i.e. radiologist 1 or radiologist 2) by the adjudicator will be the final radiology assessment for the patient. If there is no adjudication, the final radiology assessment defaults to radiologist 1. Refer to Imaging Review Charter for more details.

The local radiographic imaging assessment will be used for patient management at the site and will be compared to central assessments to evaluate concordance as described in the IDMC charter and mock tables. The local investigator assessment as captured on the CRF will be used as a sensitivity analysis for radiographic progression-free survival only.

8.1.1 Primary Efficacy Definitions

Overall Survival (OS) (months): $(\text{Date of death/censor} - \text{Date of randomization} + 1) / 30.4375$. OS is defined as the time (in months) from the date of randomization to the date of death due to any cause. If the patient is not known to have died, then OS will be censored. The censoring date is date of last contact (see Section 5), i.e. the date the patient was last known to be alive).

Radiographic progression-free survival (rPFS) (months): $(\text{Date of radiographic PD/death/censor} - \text{date of randomization} + 1) / 30.4375$. rPFS is defined as the time (in months) from the date of randomization to the date of radiographic disease progression as outlined in PCWG3 Guidelines (Scher et al 2016; protocol Appendix 7, RECIST v1.1; FDA guidance, 2007; EMA guideline, 2012) or death due to any cause.

- Note:
 - In the investigational treatment arm, a patient continues to be in the treatment period of the study on BSC/BSoC after receiving their final dose of ¹⁷⁷Lu-PSMA-617.

- Patients are at risk of the different types of rPFS events for different lengths of time:
 - RECIST v1.1 (Soft tissue) PD can occur up through last scan, which can be during long term follow-up (LTFU).
 - Bone PD can occur up to scan prior to last scan (with confirmation at last scan), which can be during LTFU.
 - Death can occur up through 24 weeks past the last study scan, or if no post treatment scans, up to 24 weeks after the first randomized treatment dose (based on the 2 missed visits censoring rule)
- Date of radiographic progressive disease (radiographic PD) event: date of the first CT/MRI/bone scan PD/death due to any cause occurs with no more than 1 immediately prior missing assessment.
 - RECIST 1.1 PD
 - Assessment in which Overall RECIST v1.1 Response is PD
 - Date of PD is date of first appearance of the new lesion(s), if applicable.
 - Bone scan PD must be confirmed as follows (rules allow for a flare effect at the first post-treatment scan). See examples in Appendix B:
 - Rule 1 (Progression at week 8 confirmed at week 16): If there are at least two new lesions on the first post-treatment scan, they must be confirmed with at least two additional lesions on the next scan (2+2 rule). The date of progression is the date of the first post-treatment scan.
 - Rule 2 (Progression at week 16 or later confirmed at next scan): For scans after the first post-treatment scan, there must be at least two new lesions relative to the first post-treatment scan (treating as a new baseline) that remain persistent (confirmed) on a subsequent scan. The date of progression is the date of the scan that first documents the second lesion compared to first post-treatment scan.
- Date of Censoring for rPFS:
 - The censoring date is the date when the last evaluable radiographic assessment (CT/MRI/bone scan) determined a lack of progression.
 - If there were no evaluable assessments, censoring occurs at the date of randomization.
 - Patients who have 2 or more consecutive missed tumor assessments immediately prior to progressive disease (PD) or death will be censored at the date of the last evaluable tumor assessment prior to those missing tumor assessments. Study scans are every 8 weeks +/- 4 days for the first 24 weeks, then every 12 weeks +/- 4 days and are scheduled relative to date of first dose of randomized treatment. Thus, subjects are considered as having 2 missed assessments if:
 - $\text{day } 117 \leq \text{study day of event scan} \leq \text{day } 229$ and time since last evaluable assessment ≥ 118 days
(2 missed visits, $117 = 16 \text{ weeks} + 4 \text{ days} + 1$; $229 = 24 \text{ weeks} + 8 \text{ weeks} + 4 \text{ days} + 1$)
 - $\text{day } 230 \leq \text{study day of event scan} \leq \text{day } 313$ and time since last evaluable assessment ≥ 146 days

(2 missed visits, 145 = 20 weeks + 4 days + 1; 313 = 24 weeks + 20 weeks + 4 days +1)

- study day of event scan \geq day 314 and time since last evaluable assessment \geq 174 days

(2 missed visits, 173 = 24 weeks + 4 days + 1)

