Note: The reference date for safety assessments during randomized treatment (e.g. adverse event onset, laboratory measurement, vital sign measurement, ECOG performance status, etc.) is the date of first dose of randomized treatment and the reference date for efficacy assessments (i.e. survival, tumor response, health related

quality of life) is the date of randomization. The reference date for all assessments in the sub-study is the date of first dose of ¹⁷⁷Lu-PSMA-617.

Baseline for a given variable will be defined as the last non-missing assessment, including unscheduled assessments, for that variable obtained prior to or on the reference date but before the first treatment dose, unless otherwise noted.

For efficacy evaluations, the last non-missing assessment, including unscheduled assessments on or before the date of randomization is taken as "baseline" value or "baseline" assessment. For RECIST/PCWG3-based endpoints using CT/MRI, and bone scans (i.e. rPFS, ORR, DCR, duration of response, PFS), a window of 28 days from the start of randomized treatment will be allowed, i.e. the investigator/central review-reported responses will be maintained and baseline considered valid if the baseline assessment is within 28 days of randomized treatment start date. In the context of baseline definition, the efficacy evaluations also include the laboratory parameters PSA, ALP and LDH, and HRQoL (e.g. FACT-P). For safety evaluations of randomized treatment (i.e. laboratory assessments, ECOG performance status and vital signs), the last available assessment on or before the date of start of randomized treatment is taken as "baseline" assessment. For vital signs where time of assessment is captured (e.g. pre-dose and post-dose vital sign), the 15 minutes pre-dose value on or before the date of start of randomized treatment is taken as "baseline" assessment. For safety evaluations of ⁶⁸Ga-PSMA-11 (i.e. laboratory assessments and vital signs), the last available assessment on or before the date of ⁶⁸Ga-PSMA-11 is taken as "baseline" assessment.

In rare cases where multiple measurements meet the baseline definition, with no further flag or label that can identify the chronological order, then the following rule should be applied: If multiple values are from the same laboratory or collected for ECGs or vital signs, then the last value should be considered as baseline.

If patients have no value as defined, the baseline result will be considered as missing.

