5.1.2 Visit Windows

For data collected at multiple time points, the scheduled collection date/time will be used to summarize the data, unless otherwise indicated. Visits are scheduled from time of previous cycle's Day 1.

Scan assessments are scheduled from the reference date (date of first dose). Scan dates are not associated with a visit number. Dates are used for analyses and patient listings.

Unscheduled assessments will not be taken into account in summary variable calculations, except for baseline assessments and unscheduled RECIST, bone scan, PSA and HRQoL evaluations for evaluating efficacy (Section 8). All measurements will be presented in the listings.

Unless otherwise indicated, if more than one measurement (a lab result for example) exists for a patient on a particular time point/visit, the last value obtained at that time point/visit will be used when summarizing the data.

Refer to protocol section 6.1 and protocol Appendix 1 for schedules of study assessments during each study period.

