- Analysis as per the primary rPFS analysis but censoring COVID-19 related deaths at the last adequate assessment prior to the death.
- An analysis as per the 'first sensitivity analysis' but censoring COVID-19 related deaths at the date of death.

For the analyses above, the patients with COVID-19 related deaths will be determined in a blinded fashion by clinical review of the data and will be documented prior to database lock.

The same analyses conventions used for the primary analyses of rPFS, as described in section 8.2.1, will be performed (without p-values).

Supportive analyses of rPFS:

rPFS will be derived in all patients randomized (FAS population) using the same conventions as described in Section 8.1.1 but will consider patients randomized before March 5, 2019 who withdrew consent from the study (i.e. no further data on radiographic progression is available) as (1) censored at time of withdrawal and (2) a rPFS event at the time of withdrawal.

The following data will be summarized using the FAS:

- (1): Number (%) rPFS events (radiographic PD, deaths) and censored, reason censored (ongoing without event, withdrew consent, event documented with two or more missed tumor assessments, adequate assessment not available)
- (2): Number (%) rPFS events (radiographic PD, deaths, withdrew consent) and censored, reason censored (ongoing without event, withdrew consent, event documented with two or more missed tumor assessments, adequate assessment not available)

Missing tumor assessments: The number of patients with at least one missing/not evaluable tumor assessment (TA) based on independent central review will be presented together with the following breakdown categories: number of patients with 1, 2, 3, 4, 5, >5 missing/not evaluable TAs. The purpose of this analysis is to gain an insight as to whether the TAs have been carried out in accordance with the protocol and to understand if any meaningful discrepancies exist between the pattern of missing assessments by treatment arms. Timing of all tumor assessments will be depicted graphically and displayed by treatment arm.

Since the planned tumor assessments are every 8 weeks in the first 24 weeks from C1D1 and every 12 weeks thereafter, the following time windows (in weeks) will be constructed for each patient from the date of randomization: (note the open parenthesis such as (12, 20] indicates that week 12 doesn't belong to this interval and week 12+1 day belongs to that interval)

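### The rPFS two-missed-scan rule allows for one ±4-day window where two apply, and its day-count origin is in conflict, so some patients with one missed scan can be censored as having missed two

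*SAP*

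**What the plan says.** **The rule (SAP 8.1.1).** "Study scans are every 8 weeks +/- 4 days for the first 24 weeks, then every 12 weeks +/- 4 days". A progression or death counts as an event if at most one assessment was missed immediately before it. With two or more missed, the patient is censored at the last evaluable assessment before the gap. With no evaluable assessment, censoring is at randomization. Scans "are scheduled relative to date of first dose of randomized treatment. Thus, subjects are considered as having 2 missed assessments if" the study day of the event scan lies in a given band "and time since last evaluable assessment" reaches the band's limit:

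| Study day of event scan | Limit since last evaluable assessment | SAP's bracketed derivation |
|---|---|---|
| 117 to 229 | at least 118 days | 117 = 16 weeks + 4 days + 1 |
| 230 to 313 | at least 146 days | 145 = 20 weeks + 4 days + 1 |
| 314 or later | at least 174 days | 173 = 24 weeks + 4 days + 1 |

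**The origin.** SAP 5 defines study day as assessment date minus reference date, plus 1. It adds that "the reference date for efficacy assessments (i.e. survival, tumor response, health related" "quality of life) is the date of randomization". SAP 5.1.2 instead says "Scan assessments are scheduled from the reference date (date of first dose"). A note in 8.1.1 on deaths with no post-treatment scan also uses first dose: such deaths count up to 24 weeks after it, and the note cites the two-missed-visits rule as the reason.

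**Lag.** Investigational-arm patients must start dosing within 28 days of randomization (protocol 3.1, SAP 3.1). No limit is stated for Cycle 1 Day 1 in control.

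**The concern.** The rule decides which progressions and deaths count in an alternate primary endpoint that is tested at 1-sided 0.004 with 364 events. The elapsed-day limits are a proxy for the number of missed scans, so they should agree with that number for every pair of scans the schedule permits. Two features suggest that they do not.

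- The limits allow one 4-day deviation, although the last scan may be early and the event scan late.
- The bands are derived from first dose but applied to a study day that SAP 5, read literally, counts from randomization. Two programmers could each follow the SAP and give the same patient a different event status.

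Duration of response (SAP 8.1.2) and PFS (SAP 8.1.3) take over the same censoring rules.

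**Working it through.** **1. The plan's own figures.** 112 + 4 + 1 = 117; 224 + 4 + 1 = 229; 140 + 4 + 1 = 145; 308 + 4 + 1 = 313; 168 + 4 + 1 = 173. All reproduce. The limits 118, 146 and 174 are each one day above the bracketed 117, 145 and 173. If the bracket is read as the last permitted day, the two agree.

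**2. Longest interval with exactly one missed scan.** Take first dose as day 1, so week w falls on day 1 + 7w, with ±4 days at each end.

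- Week 8 to 24: 112 + 8 = 120 days (limit 118)
- Week 16 to 36: 140 + 8 = 148 days (limit 146)
- Week 24 to 48, and later pairs: 168 + 8 = 176 days (limit 174)

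Example: scan on day 53 (week 8 minus 4), week 16 missed, progression on day 173 (week 24 plus 4). The interval is 173 − 53 = 120 days, so the patient is censored with one scan missed.

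**3. How much of the permitted range is affected.** Give each scan an offset of −4 to +4 whole days, which makes 9 × 9 = 81 pairs. A limit is reached when the event-scan offset minus the earlier-scan offset is at least 6: 3 + 2 + 1 = 6 pairs, or 6/81 = 7.4%. If the interval is counted with +1, it is 10/81 = 12.3%.

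**4. Origin, when a post-baseline scan exists.** The interval is a difference of two dates, so the origin affects only the band. The latest in-window week-24 scan is day 173, and it changes band only with a lag of 230 − 173 = 57 days. For week 36 it is 314 − 257 = 57. Both exceed the 28 days allowed in the investigational arm. For deaths and unscheduled scans, a randomization origin moves some events into a later band with a longer limit, which means less censoring.

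**5. Origin, when no post-baseline scan exists.** Suppose only week 8 was missed and progression is seen at week 16 with offset d. Let L be the days from randomization to first dose.

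- Counted from first dose: study day 113 + d, interval 112 + d, at most 116. None of the 9 offsets is censored.
- Counted from randomization: study day 113 + d + L, interval 112 + d + L. Censoring needs L + d of at least 6. That gives 0 of 9 offsets at L = 0, 5 of 9 at L = 6, and 9 of 9 from L = 10.
- Study day from randomization but interval from the baseline scan (7 to 28 days before dosing): 6 to 8 of 9 at L = 7, and 9 of 9 at L = 14 to 28.

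**6. Deaths with no post-treatment scan.** The note's 24 weeks is 168 days from first dose; the first band's limit is 118. With the interval counted from first dose, a death 118 to 168 days after it counts under the note and is censored under the limit.

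**7. Would longer limits be enough?** For scheduled progression scans, yes. The shortest interval between in-window scans with two missed is week 8 to 36, 196 − 8 = 188 days, so limits of 121, 149 and 177 still catch two misses. For deaths, no. Take a week-8 scan on day 57, no later scan, and death on day 175. The week-16 and week-24 windows closed on days 117 and 173, so two scans were missed. The interval is 175 − 57 = 118 days: the present limit censors this death and 121 would count it.

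**The case against.** The strongest reply is that the rule carries its own origin. Its introductory sentence, SAP 5.1.2 and the note on deaths all point to first dose, and SAP 5 is a general statement. That is the likelier intent. It does not remove the conflict, because study day is a defined term and SAP 5 names tumor response.

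The tolerance fault is also narrow. It needs one missed scan, progression at the next, and deviations totalling at least 6 of a possible 8 days. At nominal timing (112, 140 or 168 days) nobody with a post-baseline scan is affected, so the text does not support reading the rule as censoring patients with one missed scan in general.

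Safeguards exist. The first rPFS sensitivity analysis counts events regardless of missed scans, and SAP 8.2.1 tabulates censoring reasons and scan timing by arm. However, that sensitivity analysis also drops confirmation of later bone progression and adds scans not read centrally. It can neither isolate this fault nor correct the primary p-value.

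Two further criticisms do not stand. Day 117 lies inside the week-16 window, but this causes no error if both study day and interval run from first dose (step 5). The missing-scan summary in 8.2.1 sets its windows so that "the following time windows (in weeks) will be constructed for each patient from the date of randomization". With a 4-week lag, nominal weeks 8, 16, 24, 36 and 48 become 12, 20, 28, 40 and 52, still inside [0, 12], (12, 20], (20, 28], (28, 42] and (42, 54]. That summary is descriptive.

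**Conclusion.** The tolerance fault holds under either origin: intervals of 118 to 120, 146 to 148 and 174 to 176 days with one missed scan are treated as two missed, contrary to the event definition in the same section. The 7.4% is a share of an equal-weight grid of dates, not an expected share of patients.

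The origin conflict is real but conditional. For scheduled scans it changes status only if SAP 5 governs and only for patients with no post-baseline scan, chiefly those who missed week 8 and progressed at week 16. At a lag of about 10 days or more they would be censored at or near randomization. The 24-week note on deaths conflicts with the first band in any case.

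A reader might infer that the rule favours the investigational arm. Protocol 5.1.2 requires the product to be ordered at least 10 business days ahead, which would lengthen that arm's lag if ordering follows randomization. The documents do not say when the order is placed relative to randomization, give no control-arm lag, and give no rate of missed week-8 scans. As a scale only: a simulation with 371 versus 186 patients, medians of 6 and 4 months, 6 to 11 months of follow-up, and an assumed 5% to 10% of investigational patients missing only week 8 lost about 6.5 to 13 events and moved a hazard ratio of 0.668 to 0.652–0.636. That shift needs SAP 5 to govern as well as the assumed miss rate and lags. OS is not affected.

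**What to change.** In SAP 8.1.1:

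- State that study day for this rule is counted from first dose (Cycle 1 Day 1 in control).
- Replace the elapsed-day limits with a count of scheduled windows (nominal date ±4 days from first dose) that closed without an evaluable scan between the last evaluable scan and the event. Start from first dose if there is no post-baseline scan. Censor when the count is 2 or more. One definition then serves progression scans and deaths.
- If day limits are kept, use at least 121, 149 and 177 days (plain date difference) for progression scans only, with a separate rule for deaths.
- Reconcile the reference-date text in SAP 5 and 5.1.2 and the 24-week note in 8.1.1 with the chosen rule.

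The missing-scan windows in 8.2.1 can stay. The cost is SAP wording and a small programming change, with no new data.
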